#### **8.3.6. Physical Examination**

A physical examination will be performed at the timepoints specified in [Table 3](#). Full physical examination at Screening (Visit 1); brief physical examination at all other indicated visits.

### **8.3.7. Height, Body Weight, Body Composition Analysis, and Waist Circumference**

Height will be measured at Screening only. Waist circumference will be measured at all the timepoints specified in [Table 3](#), and will be measured 3 consecutive times at each time point. The Body Composition Analyzer will collect multiple measures related to body composition using BIA, including, but not limited to, weight, fat mass, lean mass, and percentage body fat, at all the timepoints specified in Table 3.

For the Body Composition Analyzer measurements, subjects should be asked to void immediately prior to measurement and should be dressed in a hospital gown with consistent under-attire for each measurement. Subjects should remove all personal items (including shoes, watches, and jewelry) and they should be weighed on a study-approved and calibrated scale for each measurement under the same conditions. The body composition analysis should not be performed when the subject is attached to any portable electronic equipment (eg, a portable ECG machine).

### **8.3.8. 12-Lead Electrocardiogram**

A 12-lead ECG will be conducted at the timepoints specified in [Table 3](#). All scheduled ECGs must be performed after the subject has rested quietly for at least 5 minutes in the supine position.

A qualified clinician will conduct ECGs and assess ECG results using equipment that has been calibrated according to the site's SOP. The following ECG parameters will be collected: pulse, RR, PR, QRS, QT, QTcF, and QT interval corrected using the Bazett formula (QTcB).

All ECGs will be evaluated by a central reader.

### **8.3.9. Structured Interviews and Questionnaires**

Brief descriptions of each of the interviews and questionnaires to be distributed are available below. All interviews and questionnaires will be administered by trained and qualified study personnel.

For assessments performed at multiple visits, every effort should be made to pair the same clinician/rater with the same subject across visits.

[Table 3](#) provides information on the timepoints at which each assessment should be administered.

#### **8.3.9.1. Rater Review**

Rater (ie, study staff) accuracy for the MINI interview at Screening will be reviewed by central raters. Rater review is necessary for mitigating inaccurate inclusion/exclusion assessments.

Rater assessments require subject interviews to be audio recorded. The audio recording will be disclosed and explained to the subject by study staff and will be disclosed in the ICF during the informed consent process. No subject will be recorded without the knowledge that a recording is being made.

### **8.3.9.2. Diagnostic Assessments**

#### **8.3.9.2.1. Mini International Neuropsychiatric Interview/Mini International Neuropsychiatric Interview for Children and Adolescents**

The Mini International Neuropsychiatric Interview 7.0 for Schizophrenia and Psychotic Disorder Studies (MINI v7.0) and the Mini International Neuropsychiatric Interview for Children and Adolescents 7.0 for Schizophrenia and Psychotic Disorder Studies (MINI KID v7.0) are short, clinician-administered, structured diagnostic interviews, with an administration time of approximately 15 minutes ([Sheehan et al, 1998](#)). The MINI v7.0 and MINI KID v7.0 have been validated against the much longer Structured Clinical Interview for DSM Diagnoses. The MINI v7.0 and MINI KID v7.0 will be administered by the PI or designee at the timepoints in [Table 3](#).

The MINI v7.0 will be conducted with subjects  $\geq 18$  years of age and the MINI KID v7.0 will be conducted with subjects  $< 18$  years of age.

### **8.3.9.3. Safety Assessments**

#### **8.3.9.3.1. Columbia-Suicide Severity Rating Scale**

The PI or designee will administer the C-SSRS according to the timepoints in [Table 3](#). The “Baseline/Screening” version of the C-SSRS will be completed at Screening ([Posner et al, 2009a](#)). The “Since Last Visit” version will be completed at all other scheduled timepoints ([Posner et al, 2009b](#)). The C-SSRS should be administered by a qualified clinician trained in assessing and managing suicidal ideation and behavior.

### **8.3.9.4. Antipsychotic Efficacy Assessments**

For assessments performed at multiple timepoints, every effort should be made to pair the same clinician/rater with the same subject across timepoints.

#### **8.3.9.4.1. Clinical Global Impressions-Severity**

The PI or designee will complete the CGI-S scale at the timepoints specified in [Table 3](#). The CGI-S measures mental illness severity. Clinicians are asked to rate subjects based on their prior experience working with individuals in a similar patient population ([Guy 1976](#)).

#### **8.3.9.4.2. Clinical Global Impressions-Improvement**

The PI or designee will complete the CGI-I scale at the timepoints specified in [Table 3](#). The CGI-I measures mental illness improvement. Clinicians are asked to rate subjects based on their prior experience working with individuals in a similar patient population ([Guy 1976](#)).

### **8.3.9.5. Other Assessments**

#### **8.3.9.5.1. Impact of Weight on Quality of Life-Lite**

Subjects will complete the IWQOL-Lite questionnaire ([Kolotkin et al, 2001](#)) at the timepoints specified in [Table 3](#).

### **8.3.10. Supportive Clinical Care**

Subjects will be offered SCC during the 12-week Treatment Period. Participation in the SCC program will be independent of study visits and based on clinical and subject preference. The SCC component modules may include individual psychotherapy, supported education services, and family education and support. Investigators and subjects will be able to select the modules to be used based on their judgment of appropriateness. The use of any or all modules will not be mandatory for each subject.

### **8.3.11. Laboratory Assessments**

#### **8.3.11.1. Drug Testing**

A urine drug test for opioids and drugs of abuse, including amphetamine/methamphetamine, phencyclidine, and cocaine, will be performed at the timepoints specified in [Table 3](#). Results must be negative at Screening (Visit 1) and Baseline (Visit 2) for the subject to be eligible for the study. Centralized drug testing will be performed at Screening (Visit 1) and local drug testing (via dipstick) at other timepoints, as specified in Table 3. The urine drug screen may be repeated at any point during the study based on the Investigator's discretion.

#### **8.3.11.2. Hematology, Biochemistry, and Urinalysis**

Fasting blood and urine samples for laboratory assessments will be collected at the timepoints specified in [Table 3](#) for specific hematology, biochemistry, and urinalysis assessments listed in [Table 4](#). Subjects will be instructed not to eat or drink anything (except water) for 8 hours before each visit where blood samples for biochemistry and hematology assessments will be collected. Samples will be collected in accordance with the site's usual procedures and analyzed by a central laboratory. Laboratory assessments may be repeated at the Investigator's discretion.

**Table 4: Clinical Laboratory Assessments**

Hematology	Biochemistry	Urinalysis
Hematocrit	General Chemistry	Bilirubin
Hemoglobin	Albumin	Color and appearance
Platelets	Bicarbonate	Glucose
Red blood cell count	Calcium	Ketones
Total and differential (absolute) white blood cell count a	Chloride	Leukocytes
	Creatine phosphokinase	Nitrite
	Glucose	Occult blood
	hs-CRP	pH
	Interleukin 6	Protein
	Lactic dehydrogenase	Specific gravity
	Potassium	Urobilinogen
	Sodium	Cotinine
	Total protein	Microscopic examination of sediment, only if urinalysis dipstick results are abnormal
	Tumor necrosis factor $\alpha$	
	Uric acid	
	Endocrine Function Test	
	Thyroid-stimulating hormone b	
	HbA1c c	
	Prolactin	
	Insulin	
	Liver Function Tests	
	Alanine aminotransferase	
	Alkaline phosphatase	
	Aspartate aminotransferase	
	Gamma-glutamyl transferase	
	Total bilirubin	
	Renal Function Tests	
	Blood urea nitrogen	
	Creatinine	
	Lipid Panel	
	High-density lipoprotein	
	Low-density lipoprotein	
	Total cholesterol	
	Triglycerides	
	Apolipoprotein B	
	Apolipoprotein A1	

Abbreviations: ANC=absolute neutrophil count; HbA1c=Hemoglobin A1c; hs-CRP=high-sensitivity C-reactive protein; PI=Principal Investigator

a At screening, if a subject has an ANC  $<1.2 \times 10^3$  per  $\mu\text{L}$ , a repeat will be allowed. However, if a subject has an ANC  $<1.0 \times 10^3$  per  $\mu\text{L}$  at any time, the PI (or designee) should discontinue the subject from participation immediately, as indicated in [Section 7.3](#).

b At Screening only; if the thyroid-stimulating hormone results indicate the value is outside of normal limits, the central lab will automatically test the same Screening visit sample and provide a free T4 and T3 analysis

c No repeats will be allowed. If a subject has HbA1c  $\geq 6.5\%$  at any time, the PI (or designee) should discontinue the subject from participation immediately, as indicated in [Section 7.3](#).

### **8.3.11.3. Urine Pregnancy Testing**

A urine pregnancy test will be administered to all women at the timepoints specified in [Table 3](#). Results must be negative for the subject to be eligible for the study at Screening (Visit 1) and Baseline (Visit 2). As highlighted in [Section 7.3](#), a positive pregnancy test result at any time will necessitate the subject's immediate withdrawal from the study. Additional follow-up may be necessary, as indicated in [Section 8.4.1](#).

### **8.3.12. Serology Testing**

A blood sample for a serology panel testing for hepatitis B surface antigen, anti-hepatitis C antibodies, and HIV will be performed at Screening only, as specified in [Table 3](#). A positive hepatitis C antibody test must be confirmed by RNA testing to be exclusionary.

### **8.3.13. Genotype Sampling**

A blood sample may be collected (at the timepoint indicated in [Table 3](#)) for evaluation of genotypes that are potentially related to response and to explore potential genetic associations with efficacy, adverse effects, symptoms, or outcomes. No other tests will be performed with these samples.

### **8.3.14. Pharmacokinetic Assessments**

Concentrations of olanzapine, samidorphan, and metabolites of interest will be determined from plasma samples collected according to the schedule in [Table 3](#). The time of last study drug administration (when applicable) and the time of each pharmacokinetic (PK) blood draw must be documented in the subject's source documents. Samples for PK analysis will be stored at  $-20^{\circ}\text{C} \pm 10^{\circ}\text{C}$ . Pharmacokinetic data from these samples may be included in a subsequent population PK analysis or other post-hoc analyses conducted outside of this study.

### **8.3.15. Randomization**

At the timepoints specified in [Table 3](#), subjects will be randomized, as outlined in [Section 9.3](#).

### **8.3.16. Drug Dispensation and Reconciliation**

[Section 9](#) provides information related to drug dispensing procedures. Study drug will be dispensed/administered at the timepoints specified in [Table 3](#). The study drug use and storage information will be explained to/reviewed with the subject.

#### **8.3.16.1. Medication Adherence and Reminder System**

A daily medication adherence monitoring and reminder system (via smartphones) may be used in this study to automatically confirm medication ingestion. After confirmation, all collected data and video recordings will be encrypted and may be transmitted to a secure centralized location, in accordance with local regulations, for further analysis, including testing for duplicate

enrollment. The captured data and video are reviewable only through a roles- and rules-restricted system ensuring privacy of the information. The system is compliant with the Health Insurance Portability and Accountability Act (HIPAA), which protects the privacy and security of healthcare information. In addition, built-in reminders and a communication system will allow real-time intervention in case of drug interruptions. Phone numbers of the patients may also be collected and stored in an encrypted manner. At no time is the phone number visible to healthcare providers or monitoring personnel. Use of this system will in no way supersede or replace the physician- and/or trial-prescribed medication protocol of the patients.

### **8.3.17. Emergency Treatment Card**

An emergency treatment card will be distributed to each subject at Screening (Visit 1) and collected at Visit 9. The card will indicate that the subject is receiving an opioid antagonist and/or olanzapine, and will include the PI's contact information, a suggested pain management plan, and information regarding opiate blockade. Subjects will be instructed to keep the card with them at all times. Study personnel will confirm that subjects have the card in their possession at each study visit.

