Starting with Week 2 (Visit 4), subjects will come for biweekly visits for the remaining 10 weeks. Study drug will be provided to subjects as coated bilayer tablets dispensed in blister packs at each visit to be taken at home (one tablet by mouth each day, preferably at bedtime). For the first week, at the discretion of the Investigator, subjects will receive 5, 10, 15, or 20 mg of olanzapine, or 5/10, 10/10, 15/10, or 20/10 mg of ALKS 3831. At the end of Week 1, for subjects initiated on 5 mg of olanzapine or 5/10 mg of ALKS 3831, the dose will be increased to 10 mg of olanzapine or 10/10 mg of ALKS 3831. For all other subjects, the dose may also be increased to either 15 or 20 mg of olanzapine, or 15/10 or 20/10 mg of ALKS 3831. Following this increase, the dose may be increased or decreased to 5, 10, 15, or 20 mg of olanzapine, or to 5/10, 10/10, 15/10, or 20/10 mg of ALKS 3831 at the Investigator's discretion. Dosing will be flexible throughout the study; however, frequent adjustments are discouraged. Dose adjustments can only be performed on-site at the study center. Subjects requiring dose adjustments between scheduled visits should arrange an unscheduled visit for the following procedures: study drug return and dispensation, adherence review, AE, and concomitant medication monitoring.

[figure not shown]
Body weight, body composition (measured by Bioelectrical Impedance Analysis [BIA] using a Body Composition Analyzer), and metabolic parameters (including fasting triglycerides, cholesterol, and glucose) will be measured throughout the 12-week treatment period. Psychiatric symptoms will be evaluated using the CGI scales. Additional assessments will include Impact of Weight on Quality of Life – Lite Questionnaire (IWQOL-Lite). A daily medication adherence monitoring and reminder system (via smartphones) may be used in this study. In addition, subjects will be asked to participate in a supportive clinical care (SCC) program during the 12-week treatment period. Participation in the SCC program will be independent of study visits and based on clinician and subject preference.

The total study duration will be approximately 20 weeks, including a 4-week Screening Period, a 12-week Treatment Period, and a 4-week Follow-up Period. Subjects completing this study will be eligible to enroll in a long-term safety study ([ALK3831-A308](#)), where it is approved by the

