#### **8.4.4. Pain Management**

Because ALKS 3831 contains samidorphan, a  $\mu$ -opioid antagonist, subjects may experience reduced or ineffective analgesia when taking an opioid analgesic agent concurrently with ALKS 3831, including several days after last dosing of ALKS 3831.

In the event of an emergency, pain management of the subject should include the following:

- Regional analgesia or use of non-opioid analgesics
- If opiate anesthesia or analgesia is required, the subject should be continuously monitored, in an anesthesia care setting, by persons not involved in the conduct of the surgical or diagnostic procedure. The opioid therapy must be provided by individuals specifically trained in the use of anesthetic drugs and the management of the respiratory effects of potent opioids, specifically the establishment and the maintenance of a patent airway and assisted ventilation

- Close monitoring by appropriately trained personnel in a setting equipped and staffed for cardiopulmonary resuscitation

For subjects requiring emergency opioid analgesics prior to dosing, the study drug should not be administered. If opioid analgesics are required after the study drug has been dosed, it may take several days for opiate sensitivity to be restored, since samidorphan functions as a  $\mu$ -opioid antagonist and could interfere with opioid-mediated pain management.

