## 9. TREATMENT OF SUBJECTS

### 9.1. Study Drug Dose and Administration

Study drugs include:

- ALKS 3831 5/10, 10/10, 15/10, or 20/10 mg, administered as a coated bilayer tablet
- Olanzapine 5, 10, 15, or 20 mg, administered as a coated bilayer tablet

For the first week, at the discretion of the Investigator, subjects will receive 5, 10, 15, or 20 mg of olanzapine or 5/10, 10/10, 15/10, or 20/10 mg of ALKS 3831. At the end of Week 1, for subjects initiated on 5 mg of olanzapine or 5/10 mg of ALKS 3831, the dose will be increased to 10 mg of olanzapine or 10/10 mg of ALKS 3831. For all other subjects, the dose may also be increased to either 15 or 20 mg of olanzapine, or 15/10 or 20/10 mg of ALKS 3831. Following this increase, the dose may be increased or decreased to 5, 10, 15, or 20 mg of olanzapine, or to 5/10, 10/10, 15/10, or 20/10 mg of ALKS 3831, at the Investigator's discretion. Dosing will be flexible throughout the study; however, frequent adjustments are discouraged. Dose adjustments can only be performed on-site at the study center.

For subjects requiring initial inpatient care, study drug will be administered orally, once daily, preferably at bedtime. Following discharge, subjects will be given study drug to take home and will be instructed to take one tablet orally, preferably at bedtime. If there are tolerability problems, dosing may be switched to another time, based on the judgment of the Investigator; frequent switching is discouraged.

Subjects will be instructed to keep all unused tablets in their blister card and to return unused tablets to the study site at their next visit. If dosing is to occur at that visit, the dose should be taken from the subject's next blister card, not from the card they are returning.

If a dose is missed or forgotten, subjects will be instructed to resume regular dosing the following night. Subjects will be instructed not to take a double dose to try to "make up" for the missed dose.

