### 10.2. Packaging and Labeling

ALKS 3831 and olanzapine will be supplied in blister packs. Blister cards will be in weekly and biweekly configurations. Weekly blister cards will contain 9 tablets, enough for 1 week of dosing, plus sufficient overage for two additional once daily doses. Biweekly blister cards will contain 16 tablets, enough for 2 weeks of dosing, plus sufficient overage for two additional once daily doses.

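### The emergency treatment card is collected at Visit 9, nominally one day after the last dose, although the protocol warns of reduced opioid analgesia for several days after ALKS 3831

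*Protocol*

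**What the plan says.** Protocol 8.3.17 sets the life of the card: "An emergency treatment card will be distributed to each subject at Screening (Visit 1) and collected at Visit 9". On content, "The card will indicate that the subject is receiving an opioid antagonist and/or olanzapine"; the card also carries the investigator's contact details, a suggested pain plan and information on opiate blockade.

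Protocol 8.4.4 describes the hazard. Opioid analgesics may work poorly or not at all when taken with ALKS 3831, "including several days after last dosing of ALKS 3831". If opioids are needed after a dose, "it may take several days for opiate sensitivity to be restored". Neither statement gives a number of days.

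Dosing is "one tablet by mouth each day, preferably at bedtime" (Protocol 8.1), for up to 12 weeks. In Protocol Table 3, drug is dispensed at Visits 2 to 8 and returned at Visits 3 to 9, so Visit 9 is a return-only visit. Completers who enter ALK3831-A308 go to Visit 1 of that study. The others enter a 4-week Safety Follow-up Period off study drug, with Visits 10 and 11 at Weeks 14 and 16.

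**The concern.** Sections 8.3.17 and 8.4.4 do not fit together. The card exists to tell a treating clinician about opiate blockade and what to do about pain. Section 8.4.4 says the blockade can outlast dosing by several days, yet the card is handed in at about the time dosing stops. A completer who does not roll over and then has an accident could reach an emergency team that has no notice of the drug.

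Section 8.4.4 treats opioid use in this setting as hazardous: it asks for continuous monitoring in an anesthesia care setting and readiness for cardiopulmonary resuscitation. A team can follow that advice only if it knows about the drug. Only subjects on ALKS 3831 are at risk, but treatment is blinded until database lock (Protocol 9.4), so the card matters for completers in both arms.

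**Working it through.** The plan gives no figure for the uncovered time, so there is none to reproduce. The day count follows from the schedule.

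**Inputs**
- Once-daily dosing for up to 12 weeks (Protocol 8.1, 9.1).
- Visit 8 target Day 71 and Visit 9 target Day 85, with Day 1 the day of first dose (SAP Table 9); window of 2 days either side (Protocol Table 3).
- Visit 10 at Week 14 (Protocol Table 3). On the same convention this is 14 × 7 + 1 = Day 99.
- Supply (Protocol 10.2): "Biweekly blister cards will contain 16 tablets, enough for 2 weeks of dosing, plus sufficient overage for two additional once daily doses". Subjects are told to "return unused tablets to the study site at their next visit" (Protocol 9.1), so no stock carries over.
- 400 subjects and 35% cumulative dropout (Protocol 14.1).

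**Gap from last dose to collection**
- Nominal: 12 × 7 = 84 doses, so the last dose is on Day 84. With Visit 9 on Day 85, the gap is 85 − 84 = 1 day.
- Latest, if dosing stops at 12 weeks: Visit 9 on Day 85 + 2 = 87, so the gap is 87 − 84 = 3 days.
- Latest, if dosing continues on the overage tablets: Visit 8 on Day 71 − 2 = 69 and 16 tablets from that evening give a last dose on Day 69 + 15 = 84. With Visit 9 on Day 87 the gap is again 3 days.

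These gaps assume no missed doses at the end; missed doses would lengthen them.

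**Days without the card while the warning may apply** (assuming that several days means 3 to 7)
- Gap of 1 day: 3 − 1 = 2 to 7 − 1 = 6 days.
- Gap of 3 days: 3 − 3 = 0 to 7 − 3 = 4 days.

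**What collection at Visit 10 would give**
- Visit 9 falls on Days 83 to 87 and Visit 10 on Days 97 to 101.
- Time from Visit 9 to Visit 10: 97 − 87 = 10 to 101 − 83 = 18 days.
- With a bedtime dose the evening before Visit 9, Visit 10 is 11 to 19 days after the last dose. This covers 3 to 7 days and leaves 11 − 7 = 4 to 19 − 3 = 16 days when the card is no longer needed.

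**Scale (order of magnitude only)**
- Completers: 400 × 0.65 = 260.
- Not rolling over, assuming 20% to 80% (no rate is given): 52 to 208. Half of these on ALKS 3831, assuming equal completion and rollover: 26 to 104.
- Uncovered ALKS 3831 time in the nominal case: 26 × 2 = 52 to 104 × 6 = 624 person-days, or 0.14 to 1.71 person-years.
- Assuming 1 to 10 emergency opioid needs per 100 person-years: 0.14 × 0.01 = 0.001 to 1.71 × 0.10 = 0.17 needs in the whole trial.

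**The case against.** The strongest case against is that this hardly matters. The last range counts needs for opioids, not harms. Harm also requires that the subject cannot or does not mention the trial and that the site is not reached. Blockade duration, rollover and event rate are all assumed. This stands, and it keeps the point minor.

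Other protections exist. Subjects who anticipate opioid use are excluded, opioids are prohibited, 8.4.4 gives a pain plan, and the investigator can break the code without waiting for approval (Protocol 9.4). Section 17.3 requires that each subject receive a copy of the signed consent form, so a reader should not infer that completers leave with no trial papers. These measures lower the risk. But a form kept at home is not a carried notice, and a code break helps only once someone knows whom to call. The consent form, the card itself and the Investigator's Brochure were not available and might say more.

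Delayed collection also has a cost: a card carried after blockade has ended could delay ordinary analgesia, and blinded olanzapine subjects have no blockade at all. This is a fair objection, and it is why the last-dose date should be on the card.

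Three stronger readings are tempting but not supported:
- A reader might count visit-window combinations to say how often the gap exceeds one day. That count depends on whether dosing stops at Day 84 or continues on overage tablets, and on treating all visit days as equally likely. The documents settle neither.
- A reader might see a contradiction in "Study personnel will confirm that subjects have the card in their possession at each study visit", since Visits 10 and 11 follow collection. The natural meaning is each visit while the card is held.
- A reader might infer that early terminators lose the card at the ET Visit, because that visit mimics the Visit 9 assessments. Section 8.3.17 does not say when their card is collected. This is a gap in the text, not a stated rule.

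**Conclusion.** The point holds as a minor safety improvement. For completers not entering ALK3831-A308, following 8.3.17 as written withdraws the only carried notice the protocol describes nominally one day after the last dose, and at most about three days after it within the visit window, while the warning in 8.4.4 still applies.

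The one-day gap follows from the dosing and visit schedule. The 2 to 6 uncovered days rest on reading several days as 3 to 7. The number of subjects and the expected events rest on further assumptions and show only that the event is rare. A reader should not infer that the trial is unsafe or that its results are compromised: no endpoint, analysis or blinding arrangement is touched. The case rests on the possible seriousness of a rare event and the very low cost of avoiding it.

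**What to change.** Amend 8.3.17 and the card as follows:

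1. For subjects not entering ALK3831-A308, collect the card at Visit 10 instead of Visit 9.
2. Change the card's wording to *is receiving or has recently received*.
3. Write the last-dose date on the card at Visit 9, or at ET, so that a clinician can judge whether blockade is still plausible.
4. State that the card is not collected at the ET Visit and that the same rule applies afterwards. The protocol does not say how long after ET Visit 10 falls, so specify the first follow-up visit at least 10 days after ET.

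The cost is a few sentences in the protocol and site instructions and a small change to the card text, with no new visit and no new data. A few cards may not be returned. Some subjects, including blinded olanzapine subjects, will carry the card for some days when it is not needed. The plan already accepts this before treatment, since the card is issued at Visit 1, up to 30 days before randomization.
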